Quality of life assessments will occur in conjunction with the clinical follow-up schedule in order to minimize missing data and to link the clinical assessments with patients' self-reported symptom burden. This design should also minimize patient and staff burden. The assessment times are fixed and are scheduled to occur as noted in [Section 18.2d](#). The time points are designed to capture acute toxicity and HRQL impact prior to treatment initiation, during planned therapy (e.g., Cycle 3, Day 1) and at the end of planned therapy (including radiation), as well as the persistence of toxicity and HRQL impact after date of registration (at 12 and 36 months). The assessment at Cycle 3, Day 1 was selected to align with a post 2 cycle disease response that will be done on the trial in the same time frame. The end-of-treatment visit after completion of planned therapy also coincides to the anticipate dose peak level of the tubulin toxins and thus, the potentially greatest risk of CIPN, as has been seen in our ongoing COG study. The 12-month after date of registration time points are important to understanding the potential resolution of acute toxicities and their impact on HRQL for these novel agents. The 36-month after date of registration time point is deliberately chosen both to assess persistence of toxicity (i.e., fatigue and neuropathy), as well as to capture HRQL in cases where salvage therapy may have been necessary in cases of failure of primary treatment on either study arm. In addition, given the unknown temporal course of immune modulation in de novo disease both with regard to control of HL and to the risk of immune-mediated toxicity, a 36-month assessment time point is thought to be important. The specification of fixed assessment times helps limit the potential to induce a dependence between the clinical and QOL outcomes, which could bias the QOL results. Study windows have been created around each of the planned assessments to avoid dependency of the treatment course (e.g., due to treatment delays).

Multiple primary endpoints will be examined, two for fatigue, and two for neuropathy. To examine the four independent endpoints with full power that includes adjustment for multiple comparisons, all 940 eligible patients will be included in the QOL analyses. To adjust for multiple comparisons, we will set alpha=.0125 based on Bonferroni.

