Neuropathy will be analyzed by arm at 1 year and at 3 years after randomization. This instrument is validated for both pediatric and adult patients. We hypothesize that patients assigned to the BV-AVD arm will have worse neuropathy over time compared to patients on the N-AVD arm, although as for fatigue, we allow uncertainty about the direction of the effect and will rely on a two-sided design. Neuropathy will be measured using the FACT/GOG-Ntx. The modified 9-item scale FACT/GOG-Ntx measures the severity of neurotoxicity on a continuous scale. A change of 3 points has been proposed as the minimally significant (i.e., clinically important) difference for this subscale. (23) Standard deviations at  $\geq 3$  months after initiation of treatment are generally about 9 points; for design purposes, we assume a more conservative standard deviation of 10 points, corresponding to an effect of 0.3 points, a small to medium effect. (24,25) Greater dropout and non-response of 25% is assumed at 1 year, and 35% at 3 years. Based on these parameters and using a two-sided two-arm normal design with alpha=.0125, there will be 93% power to detect a difference of 3 points in the FACT/GOG-Ntx at 1 year after randomization and 89% at 3 years.

Consistent with the design, the analyses of the PROMIS-Fatigue and FACT/GOG-Ntx endpoints will be conducted using multiple linear regression analysis, adjusting for stratification factors and the baseline score as covariates. See [Section 6.0](#) for stratification factors. We will also conduct longitudinal modeling of the outcome measures over time. Power for the longitudinal analysis will be greater since the addition of all available scores over time will provide more information. For longitudinal modeling, linear mixed models will be used. The potential for

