differential dropout by arm will be mitigated by reminder notifications to site investigators to encourage proper assessment and submission of forms at every required time point for all patients. Dropout patterns will be monitored on an ongoing basis. Nonetheless the potential for non-random dropout exists. Cohort plots will be prepared to examine the extent to which missing data are informative (i.e., scores are higher (worse) for patients just before their data are missing for the subsequent assessment). If there is evidence of non-random dropout, pattern-mixture models will be utilized as a sensitivity analysis. Covariates for longitudinal modeling will include intervention assignment, assessment time, their interaction, the baseline score, and the stratification factors as covariates. We will also explore differences in trajectories by categorical age (12-17 years, 18-39 years,  $\geq$  40 years).

Secondary objectives include examinations by arm of fatigue and neuropathy at the other specified discrete timepoints (fatigue: beginning of Cycle 3, and 3 years after randomization; neuropathy: beginning of Cycle 3 and time of completion of treatment). Analyses by arm at these individual assessment times will be conducted using multiple linear regression, adjusting for stratification factors and the baseline score as covariates. For all secondary analyses, no adjustment for multiple comparisons will be made, as these are considered hypothesis-generating, requiring confirmation in independent analysis.

We will also examine patient-reported health-related quality of life by arm using the PROMIS Global for pediatric and adult patients. (26,27,28) Further, we will compare the quality-adjusted survival between the study arms, using the Q-TWiST method from diagnosis to the end of follow up. Utility weights for this analysis will be obtained from the PROMIS-Global, via established crosswalk algorithms. (29)

We will describe scores on all patient-reported measures at each time period using means, standard deviations, medians, 25th-75th percentiles, minimums and maximums, histograms, frequencies, and percentages. Missing data will be explored for all variables.

h. References

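### The quality-of-life dropout sensitivity analysis depends on a check of observed scores, which can stay silent when dropout is driven by deterioration after the last visit

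*Combined protocol and SAP*

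**What the plan says.** Section 18.2g names four primary quality-of-life comparisons: fatigue after therapy and at 1 year, and neuropathy at 1 and 3 years. For PROMIS-Fatigue and FACT/GOG-Ntx, the "endpoints will be conducted using multiple linear regression analysis, adjusting for stratification factors and the baseline score as covariates". A longitudinal analysis is added: "For longitudinal modeling, linear mixed models will be used".

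On missing data, the section assumes losses of 20% and 25% for the two fatigue endpoints. For neuropathy it states: "Greater dropout and non-response of 25% is assumed at 1 year, and 35% at 3 years". It concedes the risk: "Nonetheless the potential for non-random dropout exists". It then gives a diagnostic and a rule:

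- Diagnostic: "Cohort plots will be prepared to examine the extent to which missing data are informative", with informative explained as meaning that "scores are higher (worse) for patients just before their data are missing for the subsequent assessment".
- Rule: "If there is evidence of non-random dropout, pattern-mixture models will be utilized as a sensitivity analysis".

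The section gives no threshold for what counts as evidence, no analysis that is run regardless, and no identifying assumption for the pattern-mixture models. The rule sits among the longitudinal-modelling text, and no sensitivity analysis is named for the four primary regressions.

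**The concern.** Whether dropout depends on a score already seen and whether it depends on a score never seen are different questions. The cohort plot addresses the first. A sensitivity analysis for non-random dropout exists for the second, which observed data cannot settle. Making that analysis conditional on the plot means it may be skipped in the case it is meant for.

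The visit schedule makes this realistic. Assessments are at baseline, Day 56, 4-8 weeks after therapy, 1 year and 3 years. A patient lost at the post-therapy visit was last seen at the start of Cycle 3, with four of six cycles still to come. Section 18.2g itself expects neuropathy risk to peak around the end of treatment. A patient lost at 3 years was last scheduled two years before. The trial is open-label (Section 7.1a) and the arms have different toxicities, so arm-specific loss is plausible.

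At stake are the between-arm fatigue and neuropathy results. Section 2.5 says quality of life may inform practice if PFS is similar. The PFS analysis is not affected.

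**Working it through.** **The plan's figures.** No stated figure is disputed. The FACT/GOG-Ntx power reproduces with two-sided alpha 0.0125 (z = 2.498), SD 10 and a 3-point difference:

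- 1 year: n per arm = 940 × 0.75 / 2 = 352.5; SE = 10 × √(2/352.5) = 0.753; power = Φ(3/0.753 − 2.498) = 93.1% (stated 93%).
- 3 years: n per arm = 940 × 0.65 / 2 = 305.5; SE = 10 × √(2/305.5) = 0.809; power = Φ(3/0.809 − 2.498) = 88.7% (stated 89%).

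**What the plot can see.** Let Y1 be the last observed score and Y2 the next one, in SD units with correlation ρ, so Y2 = ρY1 + e with e uncorrelated with Y1. Suppose the log-odds of dropout are linear in a driver S. The expected direction of the gap in Y1 between dropouts and stayers follows the sign of Cov(Y1, S):

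- S = Y1 (score already seen): covariance 1, so dropouts look worse.
- S = Y2 (whole unseen score): covariance ρ, so dropouts look worse, less clearly.
- S = e (deterioration not predicted by Y1): covariance 0, so no gap.
- S = Y2 − Y1 (raw change): covariance ρ − 1, which is negative, so dropouts look *better*.

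The plan counts only a worse last score as informative, so the last two drivers escape it.

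**Size.** From the documents: 940 patients, 1:1 allocation, SDs of 12 (PROMIS Fatigue) and 10 (FACT/GOG-Ntx), 25% missing. Assumed: ρ = 0.5, log-odds 0.7 per SD in one arm only, no true arm difference, and the plot formalised as a 5% t-test of Y1 in dropouts against stayers.

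| Driver of dropout | Check fires | Bias of baseline-adjusted arm difference |
|---|---|---|
| Unpredicted part, e | about 5% | about 0.12 SD (0.115) |
| Raw change | about 0% in the worse direction (about 55% two-sided) | about 0.08 SD |
| Unpredicted part, 5% missing | – | about 0.03 SD |

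In points, 0.115 SD is 0.115 × 12 = 1.4 on PROMIS Fatigue and 0.115 × 10 = 1.2 on FACT/GOG-Ntx. Against the plan's target effect of 0.3 SD, 0.115/0.3 is 38%. For e with ρ between 0.3 and 0.7, the bias is 0.08-0.15 SD.

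**A second set of assumptions.** This used four visits, cumulative loss of 20% then 25%, log-odds of 1 per SD in one arm, a one-sided 5% test, ρ from 0.3 to 0.7, and the PROMIS Fatigue SD of 12. Bias is in points, over the two follow-up endpoints; the minus sign means the affected arm looks better than it is.

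| Driver | Check fires | Bias, baseline-adjusted regression | Bias, mixed model |
|---|---|---|---|
| None (completely random) | 4-5% | about 0 | about 0 |
| Last observed score | 100% | −0.4 to −1.0 | about 0 |
| Unpredicted part, e | 9-10% | −1.4 to −2.3 | −1.4 to −2.3 |
| Whole unseen score | 76-100% | −1.5 to −2.3 | −1.3 to −2.2 |

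**The case against.** **The check is informative.** It would be easy to infer that the plot fires only when the analysis is already valid. That holds for the mixed model, but the four primary comparisons use regressions adjusted only for baseline and strata. Dropout driven by an intermediate score biases those (second table), so a positive plot is a relevant warning. When dropout follows the whole unseen score, the check fires in roughly 60-100% of runs in most settings; with the weaker one-arm slope the range over correlations 0.3-0.7 is 25-85%. This objection stands and is why the plots should be kept.

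**The silence depends on how change is defined.** The 5% rate needs the driver to be the part of the later score not predicted by the last one. Raw change is negatively correlated with the last score, so a two-sided test fires in about 99% of runs if both arms are affected and about 55% if one is. This also stands, but the gap runs opposite to the plan's definition of informative.

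**The plan never says that a flat plot proves missingness harmless.** Correct. The trigger wording is not expressly limited to the plots, dropout patterns are monitored, and reasons for non-completion are recorded (Section 15.5c). The plots are nevertheless the only diagnostic named with the trigger, and without such evidence no sensitivity analysis is required.

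**There are other safeguards.** Collection continues after early discontinuation, progression or new therapy (Sections 7.7a and 15.5), telephone or video interviews are required for patients too sick to attend, and sites are reminded. Section 18.2b reports 95% collection at follow-up in a related paediatric trial, and the assumed fatigue losses are called conservative. So 20-35% missing is a planning assumption, and at 5% the bias is small. These measures reduce missing data; they do not show how far the results depend on what is still missing.

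**Conclusion.** The point holds in a limited form. The sensitivity analysis for non-random dropout is conditional on a diagnostic that cannot rule such dropout out, and the diagnostic can stay silent when loss is driven by deterioration after the last visit. That follows from the plan's wording and needs no simulation.

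The size does rest on assumptions that the documents do not supply: the correlation, the slope, dropout that depends on outcome in one arm only, and a t-test standing in for a visual judgement. Under them the bias is about 0.12 SD at 25% missing, and about 0.03 SD at 5%.

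A reader might infer that the check never detects non-random dropout, or that the plan has no other protection against missing data. The documents and the calculations support neither. The matter concerns quality-of-life conclusions only.

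**What to change.** In Section 18.2g, replace the conditional sentence with:

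*Delta-adjusted pattern-mixture models will be fitted as a sensitivity analysis for the four primary fatigue and neuropathy comparisons regardless of the cohort plots, with deltas varied separately by arm over a pre-specified range (for example 0 to the clinically important difference of each instrument), reporting the delta at which the conclusion changes.*

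The range must be written down, or the analysis is not pre-specified. The plan already gives anchors: 3 points for FACT/GOG-Ntx and 3-5 points for PROMIS Fatigue. Keep the cohort plots as description and as a warning for the primary regressions.

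The cost is one extra analysis per primary quality-of-life endpoint, with no new data and no change to sample size or power.

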## Endocrinopathy Management Algorithm

Rule out non-inflammatory causes. If non-inflammatory cause, treat accordingly and continue immuno-oncology (I-O) therapy. Consider visual field testing, endocrinology consultation, and imaging.

[figure not shown]
Patients on IV steroids may be switched to an equivalent dose of oral corticosteroids (e.g. prednisone) at start of tapering or earlier, once sustained clinical improvement is observed. Lower bioavailability of oral corticosteroids should be taken into account when switching to the equivalent dose of oral corticosteroids.

b. GI Adverse Event Management Algorithm

## GI Adverse Event Management Algorithm

Rule out non-inflammatory causes. If non-inflammatory cause is identified, treat accordingly and continue I-O therapy. Opiates/narcotics may mask symptoms of perforation. Infliximab should not be used in cases of perforation or sepsis.

[figure not shown]
Patients on IV steroids may be switched to an equivalent dose of oral corticosteroids (e.g. prednisone) at start of tapering or earlier, once sustained clinical improvement is observed. Lower bioavailability of oral corticosteroids should be taken into account when switching to the equivalent dose of oral corticosteroids.

c. Hepatic Adverse Event Management Algorithm

## Hepatic Adverse Event Management Algorithm

Rule out non-inflammatory causes. If non-inflammatory cause, treat accordingly and continue I-O therapy. Consider imaging for obstruction.

Patients on IV steroids may be switched to an equivalent dose of oral corticosteroids (e.g. prednisone) at start of tapering or earlier, once sustained clinical improvement is observed. Lower bioavailability of oral corticosteroids should be taken into account when switching to the equivalent dose of oral corticosteroids.

\*I-O therapy may be delayed rather than discontinued if AST/ALT ≤ 8 x ULN and T.bili ≤ 5 x ULN.

[figure not shown]
\*\*The recommended starting dose for grade 4 hepatitis is 2 mg/kg/day methylprednisolone IV.

d. Neurological Adverse Event Management Algorithm

## Neurological Adverse Event Management Algorithm

Rule out non-inflammatory causes. If non-inflammatory cause, treat accordingly and continue I-O therapy.

[figure not shown]
Patients on IV steroids may be switched to an equivalent dose of oral corticosteroids (e.g. prednisone) at start of tapering or earlier, once sustained clinical improvement is observed. Lower bioavailability of oral corticosteroids should be taken into account when switching to the equivalent dose of oral corticosteroids.

e. Pulmonary Adverse Event Management Algorithm

## Pulmonary Adverse Event Management Algorithm

Rule out non-inflammatory causes. If non-inflammatory cause, treat accordingly and continue I-O therapy. Evaluate with imaging and pulmonary consultation.

[figure not shown]
Patients on IV steroids may be switched to an equivalent dose of oral corticosteroids (e.g. prednisone) at start of tapering or earlier, once sustained clinical improvement is observed. Lower bioavailability of oral corticosteroids should be taken into account when switching to the equivalent dose of oral corticosteroids.

f. Renal Adverse Event Management Algorithm

## Renal Adverse Event Management Algorithm

Rule out non-inflammatory causes. If non-inflammatory cause, treat accordingly and continue I-O therapy

[figure not shown]
Patients on IV steroids may be switched to an equivalent dose of oral corticosteroids (e.g. prednisone) at start of tapering or earlier, once sustained clinical improvement is observed. Lower bioavailability of oral corticosteroids should be taken into account when switching to the equivalent dose of oral corticosteroids.

g. Skin Adverse Event Management Algorithm

## Skin Adverse Event Management Algorithm

Rule out non-inflammatory causes. If non-inflammatory cause, treat accordingly and continue I-O therapy.

Patients on IV steroids may be switched to an equivalent dose of oral corticosteroids (e.g. prednisone) at start of tapering or earlier, once sustained clinical improvement is observed. Lower bioavailability of oral corticosteroids should be taken into account when switching to the equivalent dose of oral corticosteroids.

\*Refer to NCI CTCAE v4 for term-specific grading criteria.

18.4 Performance Status Scales

Performance Status Criteria			
Lansky performance scores are intended to be multiples of 10			
Zubrod		Lansky*	
Score	Description	Score	Description
0	Fully active, able to carry on all pre-disease performance without restriction.	100	Fully active, normal.
		90	Minor restrictions in physically strenuous activity.
1	Restricted in physically strenuous activity but ambulatory and able to carry out work of a light or sedentary nature, e.g., light housework, office work.	80	Active, but tires more quickly
		70	Both greater restriction of and less time spent in play activity.
2	Ambulatory and capable of all self-care but unable to carry out any work activities. Up and about more than 50% of waking hours	60	Up and around, but minimal active play; keeps busy with quieter activities.
		50	Gets dressed, but lies around much of the day; no active play, able to participate in all quiet play and activities.
3	Capable of only limited self-care, confined to bed or chair more than 50% of waking hours.	40	Mostly in bed; participates in quiet activities.
		30	In bed; needs assistance even for quiet play.
4	Completely disabled. Cannot carry on any self-care. Totally confined to bed or chair.	20	Often sleeping; play entirely limited to very passive activities.
		10	No play; does not get out of bed.

\*The conversion of Lansky to Zubrod scales is intended for NCI reporting purposes only.

18.5 FDG PET-CT Imaging Procedures and Image Acquisition

a. FDG-PET-CT Requirements for Participation

1. Access:

The participating center must have, or have access to, a facility with an integrated positron-emission tomography and computed tomography (PET-CT) scanner.

2. Electronic Submission

The participating center must have the ability to submit PET and CT studies electronically to the ACRIN Imaging Core Laboratory in digital DICOM format (other formats: BITMAP, JPG). Hardcopy or scanned files are not acceptable.

b. FDG-PET-CT Imaging Procedures

**Patient Preparation**

Patients must fast for at least four hours before the PET-CT scan. Oral hydration is strongly encouraged prior to and during injection of  $^{18}\text{F}$ -FDG (250-500 mL water can be given PO during the uptake period). Intravenous fluids containing dextrose or parenteral feeding should be withheld for at least 6 hours prior to the injection of  $^{18}\text{F}$ -FDG. No steroid administration is allowed for at least 7 days prior to FDG-PET imaging. Active exercise should be discouraged for at least 24 hours prior to the study. Muscle stress, tension, chewing, and movement during the uptake period should be minimized to decrease muscle uptake. Patients should not speak during the injection and uptake period. Interviews with the patient should be withheld until after completion of the imaging study.

The blood glucose level should be checked before  $^{18}\text{F}$ -FDG injection. Blood sugar (measured by glucometer) must be less than 200 mg/dL at the time of the FDG-PET-CT study. If the blood glucose level is greater than 200 mg/dL, the FDG-PET-CT imaging should be rescheduled. If the blood glucose level still exceeds 200 mg/dL on the following scheduled day for PET scanning, the patient will not be included in the analysis. Insulin administration immediately before the PET-CT study to reduce the glucose levels is not allowed. Patients with diabetes should continue to adhere to their oral agents or insulin routines. These medications should not be administered near the  $^{18}\text{F}$ -FDG injection time. In insulin-dependent patients, insulin should be administered at least 5 hours prior to the  $^{18}\text{F}$ -FDG injection. Patients with diabetes who are on diabetic medication should take their medication 4-5 hours prior to the test.

Metallic objects should be removed from the patients whenever possible. Patients should be kept in a warm waiting room prior to  $^{18}\text{F}$ -FDG injection to avoid brown adipose tissue uptake. In anxious and claustrophobic patients, administration of oral diazepam (0.06-0.10 mg/kg) is recommended 30-40 minutes prior to the initiation of the imaging study.

Weight (kg), height (cm), blood glucose (mg/dL), and the date and time of chemotherapy, glucose levels and colony stimulating factor administration (e.g., GCSF, GMCSF) should be recorded prior to the injection of  $^{18}\text{F}$ -FDG.

The dose of F-FDG should be based on the scanner manufacturer's recommendation (per institutional procedure). A 10-20 mL saline flush is recommended in reducing the venous retention of F-FDG. The patient must wait at least 60 minutes (+/-10 minutes) prior to the initiation of the PET-CT acquisition for all PET-CT scans (both pre-and post-therapy scans). The imaging wait from injection period should be kept with a minimal variation of 10 minutes among patients. The wait period should not be shorter than 50 min and longer than 75 minutes at baseline. The time difference between baseline and other time points (i.e. interim and end of therapy) should **not** exceed 10 minutes.

The imaging will start after voiding the bladder. 150-200 mL of water should be given to the patient immediately prior to the study acquisition before they are positioned on the table to distend stomach and avoid physiologic stomach uptake.

c. FDG-PET-CT Image Acquisition

Patients should be positioned on the table in a headfirst, supine position with arms elevated above the abdomen to reduce beam-hardening artifacts at the level of the liver. The use of IV and oral contrast is at the discretion of each institution. However, IV-contrast CT acquisition is recommended to follow PET imaging acquired with non-contrast CT to avoid variations in FDG uptake in the blood pool and the tumor.

If IV contrast is not used, CT should be acquired using a current of not less than 120 mA/second to allow for sufficient resolution for definition of anatomic structures. Immediately after CT scanning, a PET emission scan will be obtained.

The PET-CT scan should cover at least from the mid skull to the 1/3 proximal femurs. The time/bed position should be in accordance with the manufacturer's recommendations for optimal imaging.

It is critical that follow-up PET-CT scans be performed in an identical way to the baseline scan, with the same scanner, same scan direction (skull to thighs or thighs to skull), and consistent arm positioning (arms up or arms down).

